#### 4.2 Exclusion Criteria

- Not within defined age range
- Current diagnosis of or using medication for:
  - Severe allergies
  - o Asthma
  - Exercise-induced asthma
  - Exercise-induced bronchoconstriction
- Pulmonary function test considered to be abnormal (defined as forced vital capacity (FVC) <80% of predicted, forced expiratory volume in one second (FEV1) <80% predicted, and/or FEV1/FVC ratio >5% of the predicted ratio)
- Hypertension during screening (systolic blood pressure >139 or diastolic blood pressure >89)
- Current tobacco or electronic cigarette use or consistent use within the last 2 years
- A contraindication for use of cetirizine HCI:
  - $\circ\,$  Previous adverse reaction to cetirizine HCl or a similar medication
  - Allergy to the food additives E218 or E216
  - An intolerance to or inability to absorb some sugars, such as lactose or sorbitol
  - Liver or kidney failure
  - Epilepsy or similar condition
  - A condition that makes urinating difficult
  - o Use of midodrine or ritonavir
- Are pregnant or could possibly be pregnant by self-report
- Subjects with current, irregular menstrual cycles (amenorrhea) or who had irregular menstruation patterns for greater than one year
- People who answer 'yes' to any of the pre-participation screening questions on page one of the PAR-Q+ questionnaire.

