Those selected for further study will visit the Human Performance Laboratory on two occasions separated by at least 48 hours and no more than 60 days. Apart from receiving a placebo (PL) or drug treatment (cetirizine HCl, CH) prior to exercise, participants will perform identical protocols on each visit to the laboratory. Participants will report to the lab and consume either a placebo or CH pill, followed by a health history update questionnaire and their resting pulmonary function will be measured. Participants will then complete a self-selected warm-up that will be standardized across all testing sessions, followed by instrumentation. The exercise protocol beings with a progressive swimming test to maximum aerobic capacity ( $\dot{V}O_{2max}$ ) in a swimming flume, followed by two constant load work bouts at approximately 70 and 85% of the previously recorded HRmax while peripheral capillary oxyhemoglobin saturation (SpO2) is continuously monitored. Participants will receive a 20-min break between each work bout. Drug treatments will be assigned in a double-blind, randomized crossover fashion such that each participant receives each treatment. Concentrations of plasma histamine, whole blood histamine, and histamine release will be assessed from pre- and post-exercise blood samples.

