- Experimental Trials (visits 3 and 4): Prior to all testing sessions, participants will be asked to abstain from allergy medication for 48 hours, intense exercise for 24 hours, caffeine and alcohol for 12 hours, and food for 2 hours. Prior to the sessions 3-4, participants will also be asked to consume a similar diet the night before and day of each testing session. Women participants will be asked to self-identify when their last menses occurred. In order to prevent sex differences caused by fluctuations in hormone across the menstrual cycle, women participants will only be tested during the first 7 days following menstruation (when estrogen and progesterone hormones are at their lowest levels) for sessions 2-4 (Allen et al., 2016). Apart from receiving a placebo (PL) or drug treatment (CH) prior to exercise, participants will perform identical protocols on each visit to the laboratory. Participants will report to the lab and consume either a placebo or CH pill, followed by a health history update questionnaire and their resting pulmonary function will be measured. Participants will then complete a self-selected warm-up that will be standardized across the two testing sessions, followed by instrumentation. The exercise protocol beings with a progressive swimming test to maximum aerobic capacity (VO2max) in a swimming flume, followed by two constant load work bouts at approximately 70 and 85% of the previously recorded HRmax while peripheral capillary oxyhemoglobin saturation ( $S_pO_2$ ) is continuously monitored. Participants will receive a 20-min break between each work bout. Drug treatments will be assigned in a double-blind, randomized crossover fashion such that each participant receives each treatment. Concentrations of plasma histamine, whole blood histamine, and histamine release will be assessed from a venous blood draw one hour prior to commencement of the aerobic capacity test, and immediately following the aerobic capacity test and each of the two constant load bouts.

**8.0 Study Calendar** The following procedures will be undertaken during the visits.

Table 1: Description of Stud	v Procedures that will take	place on each visit to the laboratory.
	y i roccuures that will take	

STUDY PROCEDURES	Screening (Visit 1)	Selection Exercise Test (Visit 2)	Experimental Trials – Randomized Crossover (Visits 3-4)	
			Placebo	Cetirizine HCI
Height	Х		Х	Х
Weight	Х		Х	Х
Heart rate	Х		Х	Х
Urine specific gravity		Х	Х	Х

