• Bacterial/Viral Transmission: There is a risk of germ transmission through shared face masks, despite cleaning and treatment in an anti-bacterial solution following each use. Researchers will thoroughly scrub all shared equipment with anti-bacterial detergent and warm water immediately following use.

- Exercise: Submaximal (low and moderate effort) and maximal (all-out effort) exercise tests of healthy individuals, as described by the American College of Sports Medicine, present little risk and do not require medical clearance for individuals under the age of 40. Potential risks and/or discomforts can include episodes of temporary light-headedness, chest discomfort, leg cramps, occasional irregular heartbeats, and abnormal blood pressure responses. The risk of heart attack, although minor, (approximately 1 to 2 in 10,000) does exist. One death occurs for roughly every 880,000 man hours of submaximal exercise in apparently healthy individuals.
- Drowning: There is a risk of drowning during swimming exercise. All participants have undergone many years of swimming training. During the Selection Exercise Protocol, lifeguards from Campus Recreational Sports will be present. During the Experimental Trials, swimmers will be closely monitored by researchers, at least one of whom has completed safety training in accordance with USA Swimming coaching standard.
- Drug administration:
  - Cetirizine HCI: Serious side effects of cetirizine HCI ingestion are exceedingly rare, and in very rare cases subjects can experience anaphylaxis. Cetirizine HCI can have adverse reactions with midodrine (low blood pressure medication), ritonavir (an HIV treatment), and could exacerbate symptoms of any medication that can cause drowsiness, dry mouth, or infrequent urination. Mild side effects of cetirizine HCI include drowsiness, headaches, dry mouth, nausea, dizziness, stomach pain, diarrhea, sore throat, cold-like symptoms of the nose, itching, paresthesia in the hands or feet, and feeling agitated. We have previously used cetirizine HCI in the following projects in our lab:
  - IRB #1706871260: The Individual Exercise Performance Response to Altitude: Implication for the Warfighter (PI: [name]; Publication in progress)

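### At Visits 3 and 4 the capsule precedes the health-history update, so a new cetirizine contraindication reported on that form could stop the swim but not that visit's dose

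*Combined protocol and SAP*

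**What the plan says.** Section 5.0 (Study Design) and Section 7.0 (Timeline of procedures, Experimental Trials) describe Visits 3 and 4 with the same sentence: "Participants will report to the lab and consume either a placebo or CH pill, followed by a health history update questionnaire". It goes on to say that "their resting pulmonary function will be measured"; warm-up, instrumentation and the swimming tests come after that. The drug administration item in Section 7.0 places the capsule 60 minutes ahead of testing. It is either empty or holds 10 mg of cetirizine.

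The health history update item in Section 7.0 gives the form's purpose as confirming that nothing in the swimmer's health history has changed. Section 11.0 names an excluding change in health history as a possible reason for a researcher to withdraw a swimmer. Section 4.2 has a specific list of cetirizine contraindications, among them a previous reaction to the drug, liver or kidney failure, epilepsy, difficulty urinating, and "Use of midodrine or ritonavir". The two experimental visits are "two occasions separated by at least 48 hours and no more than 60 days".

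**The concern.** A contraindication list does its work only if it is consulted before the drug is swallowed. In the written order the form comes between the dose and the swim. It can therefore protect the swimmer from exercising with a new problem, but not from that visit's capsule. The visits may be weeks apart, so a change since the last update is possible.

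What is at stake is mainly participant safety: a swimmer with a newly reported contraindication may already have taken an active dose. There is also a small consequence for the data. A lasting exclusion loses the swimmer in either order. A temporary one, found after dosing, turns a visit that could have been rescheduled undosed into a dosed visit without a swim.

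**Working it through.** No power, alpha or event figure is involved, so the check compares what different sections say about order and about other safeguards.

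1. **Order of steps.** Sections 5.0 and 7.0 give: arrive, capsule, health-history update, spirometry, warm-up, instrumentation, graded test. Because the two sections share one sentence, the second is a repeat and not independent confirmation, but nothing elsewhere gives a different order.

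2. **Is the form placed earlier anywhere?** The health history update item in Section 7.0 says the form is filled in at every visit. That is compatible with completion on arrival, but it does not place the form relative to the dose. The two places that do so put the capsule first.

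3. **Does another check precede the dose?**
 - Table 1 (Section 8.0) marks the full health history questionnaire and blood pressure for Visit 1 only.
 - Section 4.2 excludes anyone answering yes on page one of the PAR-Q+, but no repeat is described at Visits 3 and 4.
 - Spirometry is repeated, and "Pulmonary function test considered to be abnormal" is an exclusion, but it also follows the capsule. Section 4.2 lists it separately from the cetirizine contraindications.
 - "Women participants will be asked to self-identify when their last menses occurred". This applies to women only. Because testing is confined to a 7-day window, the date is probably known when the visit is booked, which gives some cover against dosing in pregnancy. It does not address the drug contraindications.
 - Swimmers are asked to "abstain from allergy medication for 48 hours" beforehand. This reduces overlap with other antihistamines but is not a review of health history or of other medicines.
 - Section 9.0 has a physician instruct researchers on giving the drug and requires continuous safety monitoring of each participant. Neither provision specifies a check before dosing.

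4. **Exposure.** Section 5.0 selects twelve swimmers, and each takes one capsule at each of two visits: 12 × 2 = 24 capsules, of which 12 × 1 = 12 are active. Hypothesis 3 in Section 12.0 gives 12 for the experimental and control cohorts pooled, and Section 17.1 also gives 12. If the four controls in Section 12.0 are instead additional, the count is (12 + 4) × 2 = 32 capsules, 16 of them active.

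5. **Frequency.** The documents give no rate at which new contraindications arise between visits, and none is assumed here. The counts in step 4 show how often the order applies, not how many doses would be affected.

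Result: as written, a new contraindication reported on the update comes to light after that visit's dose and before the swim, and no other described step puts a health-history or medication review ahead of the capsule.

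**The case against.** The strongest reply is that the exposure is very narrow. Each swimmer takes a single 10 mg active dose, the placebo is an empty capsule, and Section 9.0 describes serious side effects as extremely uncommon. Many Section 4.2 exclusions, such as age, tobacco use and blood pressure, are not listed as cetirizine contraindications. Those that are would seldom arise anew in screened competitive swimmers. Physician instruction and safety monitoring are also in place. All of this stands and limits the point to a minor one. It does not explain why the form should follow the dose.

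A reader might go further in three ways that the documents do not support.

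- *That the update would detect any new contraindication or interacting medicine.* The form is an attachment (Section 17.2) that is not reproduced, so its questions cannot be checked. The point holds for whatever is reported on it.
- *That the dose should also be held for every medicine covered by the Section 9.0 warning that cetirizine* "could exacerbate symptoms of any medication that can cause drowsiness, dry mouth, or infrequent urination". Section 4.2 does not exclude that whole class. A hold for new use would sit oddly beside eligibility for existing use, and it could cost a swimmer from a sample of 12. That is a separate eligibility question, unrelated to the order of steps.
- *That Visit 2 handles the form better.* No drug is given at Visit 2, and the form precedes the swim at every visit, so the comparison shows nothing about dosing.

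**Conclusion.** The point holds as a minor one. The written order means the update cannot prevent that visit's possibly active dose, and no other stated check before dosing fills the gap. This rests on two assumptions: that staff follow the sentence as written, and that a swimmer with a relevant change would report it on the form.

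The size is one active dose per swimmer, at a low but unquantified risk. The documents do not support a claim that harm is likely or that the trial's conclusions are threatened. The case for change is that the correction is almost free. It is best labelled a cheap improvement.

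**What to change.** Reorder the shared sentence in Sections 5.0 and 7.0. On arrival the swimmer completes the health-history update and a blinded team member reviews it. Only then does the dosing researcher described in Section 6.0 give the capsule, still 60 minutes before testing. A blinded reviewer keeps the decision to dose independent of the treatment assigned for that visit.

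State that the capsule is withheld if the update shows a new exclusion. If the problem is temporary, reschedule, keeping Visits 3 and 4 within 60 days of each other and women within their 7-day window. Spirometry may stay after the capsule, because an abnormal result is not among the listed cetirizine contraindications and can still stop the swim.

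The cost is one reordered sentence in two places, a short withholding rule, and arrival a few minutes earlier at each of the two visits. Dose, dose-to-test interval, blinding and analysis are unchanged.

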#### 9.0 Reportable Events

Safety will be constantly monitored during all data collection activities. This will occur on a participant-by-participant basis. If a suspected adverse event occurs, the principal investigator will immediately report to the IRB and cooperate with the IRB in any necessary investigation. All safety data will also be reviewed in weekly lab meetings, particularly as it relates to changes to the risk-benefit ratio.

If any of the following adverse events, which are specific to the procedures conducted in this study, were to occur, they will be reported within 5 business days to the IRB using standard operating procedures.

- Infection at venous blood draw site
- Loss of consciousness or fainting
- Adverse drug reaction
- Loss of confidentiality
- Injury requiring hospitalization
- Death

Other events deemed as events occurring outside the criteria above will be reported to the IU IRB reported within 5 business days using standard operating procedures. If any event occurs that would potentially impair the health of the subject, the experiment will be halted, and the IRB will be notified.

Any incident, experience, or outcome that meets all the following criteria will also be reported:

(1) unexpected (in terms of nature, severity, or frequency) given

- a. the research procedures that are described in the protocol-related documents, such as the IRB-approved research protocol and informed consent document; and
- b. the characteristics of the subject population being studied;
- (2) related or possibly related to participation in the research (in this guidance document, possibly related means there is a reasonable possibility that the incident, experience, or outcome may have been caused by the procedures involved in the research); and
- (3) suggests that the research places subjects or others at a greater risk of harm (including physical, psychological, economic, or social harm) than was previously known or recognized.

Subjects will be informed of possible risks before consenting to participate through the informed consent document. Details of risks and discomforts for the procedures, and steps taken to lessen the probability and/or magnitude of these risks are noted below.

• Bacterial/Viral Transmission: There is a risk of germ transmission through shared face masks, despite cleaning and treatment in an anti-bacterial solution following each use. Researchers will thoroughly scrub all shared equipment with anti-bacterial detergent and warm water immediately following use.

- Exercise: Submaximal (low and moderate effort) and maximal (all-out effort) exercise tests of healthy individuals, as described by the American College of Sports Medicine, present little risk and do not require medical clearance for individuals under the age of 40. Potential risks and/or discomforts can include episodes of temporary light-headedness, chest discomfort, leg cramps, occasional irregular heartbeats, and abnormal blood pressure responses. The risk of heart attack, although minor, (approximately 1 to 2 in 10,000) does exist. One death occurs for roughly every 880,000 man hours of submaximal exercise in apparently healthy individuals.
- Drowning: There is a risk of drowning during swimming exercise. All participants have undergone many years of swimming training. During the Selection Exercise Protocol, lifeguards from Campus Recreational Sports will be present. During the Experimental Trials, swimmers will be closely monitored by researchers, at least one of whom has completed safety training in accordance with USA Swimming coaching standard.
- Drug administration:
  - Cetirizine HCI: Serious side effects of cetirizine HCI ingestion are exceedingly rare, and in very rare cases subjects can experience anaphylaxis. Cetirizine HCI can have adverse reactions with midodrine (low blood pressure medication), ritonavir (an HIV treatment), and could exacerbate symptoms of any medication that can cause drowsiness, dry mouth, or infrequent urination. Mild side effects of cetirizine HCI include drowsiness, headaches, dry mouth, nausea, dizziness, stomach pain, diarrhea, sore throat, cold-like symptoms of the nose, itching, paresthesia in the hands or feet, and feeling agitated. We have previously used cetirizine HCI in the following projects in our lab:
  - IRB #1706871260: The Individual Exercise Performance Response to Altitude: Implication for the Warfighter (PI: [name]; Publication in progress)

In order to help further mitigate the risk of drug administration, a board-certified physician, [name], MD, will acquire the pharmaceuticals for the project and will instruct researchers on best practice for drug administration. He will not oversee any other aspects of the study.

- Venous blood sample: Participants will likely experience discomfort during venous blood draws and in rare circumstances may feel lightheaded or faint. This risk will be minimized by the venipuncture always occurring in the semi-recumbent or supine position. There is a rare risk of infection following venous blood draws. This risk will be minimized by blood draws only being conducted by trained laboratory personnel.
- Loss of confidentiality: There is a potential risk for loss of confidentiality. This risk will be alleviated by only using de-identified information.

- Electricity and Water: There is a risk of operating electrical equipment in proximity to water. All equipment that is connected to an electrical outlet will never be suspended above the pool and will be secured with safety straps in a fashion that will not allow their entry into the pool. The Cosmed K5 is battery-powered and will be the only device suspended above the water (during Experimental Trials only). The device will be connected by multiple metal components to a steel guide wire connected to a steel frame over the pool (see Figure 3).
- Other risks: There may be other risks that we cannot predict.

#### **10.0 Data Safety Monitoring**

The primary investigator is responsible for the data and safety monitoring. In addition, [name], a faculty member within the Department of Kinesiology, will serve as an independent data safety monitor for the study. Data quality, subject recruitment, accrual, retention, outcome and adverse event data will be monitored on a weekly basis.

Data will be monitored by subject number. Thus, analysis of data will be performed without any identifying features to individuals. Statistical software will be used to analyze data for significance. Results will be reported through traditional scientific outlets such as peerreviewed manuscript and presentations at national and international meetings. Communication with the IRB regarding safety will be reported directly by the principal investigator.

#### **11.0** Study Withdrawal/Discontinuation

Subjects can voluntarily withdraw from the study at any time by contacting any of the researchers on the study via any available means (personal contact, email, phone, etc.). If a researcher on the project wishes to withdraw a subject from the study, they will contact the subject directly (personal contact, phone, email, etc.). Possible indications for withdrawal by a researcher include a change in their health history that excludes them from participation and an inability to keep appointments or follow or understand the rules of the protocol. Data collected up to the time of withdraw (either voluntary or by the study team) may be used for analysis.

#### **12.0** Statistical Considerations

Sample size justification was conducted using data from a study with a similar design (Coyle and Stager, 2001) which compared the effect of diphenhydramine HCI (a competitive inhibitor to histamine similar to CH) to a placebo on  $S_aO_{2ear}$  in male cross-country runners running at 70, 80, 90, and 100% of  $\dot{V}O_{2max}$ . A depiction of the study's data can be found in Table 2 below.

	Intensity (% VO 2max )					
Treatment	70	80	90	100		
Placebo	93.7 ± 0.7%	93.4 ± 2.5%	93.0 ± 2.5%	89.8 ± 3.1%		
Diphenhydramine HCI	96.5 ± 1.2%	96.2 ± 1.0%	95.8 ± 1.2%	94.2 ± 1.8%		

### Table 2: SaO2ear data from Coyle, 2001

A two-way (treatment x intensity) ANOVA using these data produced a Cohen's *f* of 1.22 for the treatment main effect. Therefore, it was determined that using an a priori  $\alpha$  value of 0.05, an estimated twelve subjects are necessary to achieve a power of 0.80. The sample size calculation was conducted using G\*Power 3.1.9.7 (ANOVA: Fixed effects, special, main effects and interactions). Due to the randomized crossover design, all twelve subjects (n = 6 men, n = 6 women) will complete all experimental treatments (PL and CH) at all intensities (70, 85, and 100% of  $\dot{VO}_{2max}$ ).

Previous investigations (Anselme et al., 1994; Mucci et al., 2001) have observed a strong, positive, and significant (r > 0.7; p < 0.05) correlation between  $\Delta$ %H ( $\dot{V}O_{2max}$  - rest) and  $\Delta P_aO_2$  (rest -  $\dot{V}O_{2max}$ ). Using a regression equation ( $\Delta$ %H = 0.0444( $\Delta P_aO_2$ ) - 0.1137; r = 0.80) from Anselme and colleagues (1994), a conservative estimate that a  $\Delta P_aO_2 > 10$  mmHg represents EIAH (Prefaut et al., 2000), we intend to recruit participants for the experimental trials who experience a  $\Delta$ %H > 0.33 during the Selection Exercise Protocol. However, should this inclusion criterion not be met by at least eight subjects, those experiencing the highest  $\Delta$ %H during the Selection Exercise Protocol will be recruited instead.

For proof of principle that EIAH can be prospectively identified using  $\Delta$ %H, a small control group (n=2 men, n=2 women) will also be recruited. For this group, we intend to recruit participants who exhibit the lowest  $\Delta$ %H during the Selection Exercise Protocol. These participants will complete both conditions of the experimental trials.

Insufficient data exist to establish a prevalence rate of EIAH among endurance athletes. Attempts have been made to establish prevalence rates in cyclists (Powers et al., 1988) and runners (Constantini et al., 2017), however no such data exist for swimmers. Estimates of prevalence rates range from approximately 70% (Constantini et al., 2017) in highly-trained endurance runners to 32% (Coneys et al., 2011) in untrained individuals. As prevalence rates of EIAH have been demonstrated to increase with aerobic training status (Dominelli and Sheel, 2019), it is likely that the true prevalence of EIAH in highly-trained swimmers is between these values. Therefore, to ensure enrollment of an adequate number of swimmers who experience EIAH, a prevalence estimate of 50% will be utilized. Using a binomial distribution and a target of 8 EIAH-afflicted highly-trained swimmers, recruiting 26 swimmers (n = 13 men, n = 13 women) for the Selection Exercise Protocol provides a >95% probability that the population will contain at least 8 EIAH-afflicted highly-trained swimmers. In order to account for potential participant withdrawal, we anticipate recruiting no more than 30 individuals.

Prior to conducting statistical analysis all data will be visually inspected for normality and potential outliers using kernel density and quantile-quantile plots. Summary statistics of the mean, standard deviation, median, and range will be calculated for all variables of interest.

*Hypothesis 1*. EIAH has been previously defined by a decrement in  $S_pO_2$  of  $\ge 5\%$ . Should a participant experience this during submaximal or maximal exercise, the hypothesis will be confirmed.

*Hypothesis 2.* Prior to analyses, any carry-over effect will be identified using a two-way linear mixed model (visit order x time), independent of the drug treatment (placebo, or cetirizine HCI). If a carry-over effect is observed, a regressor for visit order group will be included in all subsequent analyses.

In order to test for potential differences in the dependent variables of interest, linear mixed models will be used including random effects for subject, subject within-treatment, and subject within-intensity to account for the repeated measures design. Treatment (PL and CH), intensity (70, 85, and 100% of  $\dot{V}O_{2max}$ ) and the interaction between treatment and intensity will be included. Main effects and interactions will be tested using *F*-tests from a two-way ANOVA. Statistical significance will be assessed using a pre-determined  $\alpha$  level of 0.05. Where significant main effects or interactions are observed, estimated marginal means will be used to test for differences in the drug conditions and adjusted for multiple comparisons using Dunnett's method.

*Hypothesis* 3. The correlation between the change in histamine release ( $\Delta$ %Hpre-%Hpost) and the change in SPO2 at  $\dot{V}O_{2max}$  ( $\Delta$ SPO2rest-SPO2@100%) will be assessed in the pooled experimental and control cohorts (n=12) by a Pearson correlation coefficient using a predetermined  $\alpha$  level of 0.05.

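### The power of 0.80 for twelve subjects comes from an independent-groups ANOVA, not from this crossover; the derivation of f = 1.22 is not shown, and the Aim 2 model has no term for the four low-release controls

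*Combined protocol and SAP*

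**What the plan says.** Section 12.0 bases the sample size on an earlier study of diphenhydramine against placebo in male runners "running at 70, 80, 90, and 100% of" maximal oxygen uptake (Table 2). A two-way ANOVA on those data is said to give a Cohen's f "of 1.22 for the treatment main effect". From this, at alpha 0.05, "an estimated twelve subjects are necessary to achieve a power of 0.80". The G*Power routine is named as "ANOVA: Fixed effects, special, main effects and interactions". The number of groups and the numerator degrees of freedom (df1) entered are not given.

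The same paragraph calls the trial a randomized crossover in which "all twelve subjects (n = 6 men, n = 6 women) will complete all experimental treatments", at three intensities. Under Hypothesis 2 the planned analysis is a linear mixed model with "random effects for subject, subject within-treatment, and subject within-intensity" and fixed effects for treatment, intensity and their interaction.

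On who the swimmers are, Section 12.0 gives "a target of 8 EIAH-afflicted highly-trained swimmers" and adds that "a small control group (n=2 men, n=2 women) will also be recruited". The controls are those with the lowest change in histamine release, and they complete both conditions. Pooling of the two cohorts to n = 12 is stated only for the correlation in Hypothesis 3.

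**The concern.** The power statement describes a different kind of experiment from the one planned. In an independent-groups routine, 12 means twelve separate observations spread over the cells, and treatment is tested against between-observation error. In this trial there are 12 × 2 × 3 = 72 repeated values, and treatment is tested against the variation between swimmers in their response to treatment: 11 error df with 12 swimmers, 7 with 8. Power then depends on the within-swimmer correlation, which the plan does not mention. A reader therefore cannot tell what difference Aim 2 can detect.

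Nor can a reader tell in whom. A third of the twelve are chosen for showing the least histamine release. On the plan's own rationale they may respond less to a histamine blocker, and a single treatment effect across all twelve would average over that difference.

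**Working it through.** **1. The plan's figure.** Routine as named: noncentral F, λ = f²N, df2 = N − number of cells, f = 1.22, alpha 0.05.

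| Cells | df1 | Power just below | Smallest N reaching 0.80 |
|---|---|---|---|
| 8 (2 × 4, earlier study) | 1 | 0.764 at N = 11 | 12 (0.878) |
| 6 (2 × 3, this trial) | 1 | 0.687 at N = 9 | 10 (0.818) |
| 6 (2 × 3) | 2 | 0.746 at N = 11 | 12 (0.829) |

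So 12 is reproducible. For a treatment main effect (df1 = 1) it is consistent with the earlier study's eight cells. In that layout there are 12/8 = 1.5 observations per cell and 12 − 8 = 4 error df.

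**2. f from Table 2, reading ± as an SD (the table does not label it).** The drug-minus-placebo differences are 2.8, 2.8, 2.8 and 4.4, mean 3.2. The eight squared SDs sum to 29.72, so the pooled SD is √(29.72/8) = 1.927. Then f = (3.2/2)/1.927 = 0.83. To turn this into 1.22 through a within-subject correlation ρ, solve 0.83/√(1 − ρ) = 1.22, which gives ρ ≈ 0.54. No correlation is given. At f = 0.83 the eight-cell routine would have power of about 0.58 at N = 12 and would need 16.

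**3. Paired power at a single intensity.** Difference 3.2 and SD 1.927 from Table 2. The correlation r between a swimmer's placebo and cetirizine values is assumed. SD of the difference = 1.927 × √(2(1 − r)); two-sided paired test at 0.05.

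| | r = 0 | r = 0.3 | r = 0.5 |
|---|---|---|---|
| SD of difference | 2.73 | 2.28 | 1.93 |
| 8 swimmers, all responding | 0.81 | 0.92 | 0.98 |
| 12 swimmers, all responding | 0.96 | 0.99 | >0.99 |
| 8 responding + 4 controls with no effect, pooled | 0.58 | 0.71 | 0.82 |

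The last row is from 200,000 simulated trials per entry, with a one-sample t-test on the 12 differences.

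**4. Pooled power for the average over three intensities.** The SD of the difference is multiplied by √((1 + 2c)/3), where c is the assumed correlation among a swimmer's three cetirizine-minus-placebo differences. With no effect in the controls:

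| | r = 0 | r = 0.3 | r = 0.5 |
|---|---|---|---|
| c = 0 | 0.92 | 0.97 | 0.99 |
| c = 0.9 | 0.60 | 0.73 | 0.84 |

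**5. Dilution of the estimate.** If the controls have a fraction k of the effect, the pooled estimate is (8 × 3.2 + 4 × k × 3.2)/12. This is 2.13 for k = 0, 2.40 for k = 0.25 and 2.67 for k = 0.5.

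**The case against.** Four points can be made for the plan.

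- **The number of subjects is not at risk from the routine.** A paired calculation gives at least 0.81 with only eight swimmers, even at r = 0 and with the smaller f. This stands. A reader might infer that the trial is underpowered, and the documents do not support that.
- **The eight-cell layout is an inference.** Neither the number of groups nor df1 is stated, and six groups with df1 = 2 also returns 12, although that is not a treatment main effect. This stands too. The documents establish the independent-groups routine, not that the earlier study's layout was entered.
- **f = 1.22 may be sound.** The planners may have had individual data and computed a repeated-measures f. A reader might infer instead that it came from an ANOVA on the eight printed means, since omega-squared of 0.598 there gives √(0.598/0.402) ≈ 1.22. That is one back-solved route; eta-squared on the same means gives 1.26. What can be said is that the derivation is not shown and that the printed figures do not lead to 1.22 without a further assumption.
- **The analysis set is not wholly open.** The reference to all twelve subjects in the power paragraph makes pooling the natural reading. That is fair, but it is not stated for Aim 2, and the model still has no cohort term. The documents give no figure for the effect in controls, so zero effect is an extreme case and not a forecast.

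**Conclusion.** The concern holds as a mismatch between the power method and the design, not as an arithmetic error: 12 is reproducible from the routine named. The stated 0.80 is not the power of this crossover, and the derivation of f is missing.

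The mismatch alone has little practical effect. If all swimmers respond, and a 3.2-point difference with SD 1.93 carries over from runners on another antihistamine, both 8 and 12 are adequate across the correlations examined.

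The handling of the controls matters more. With no effect in them, the estimate falls by a third, from 3.2 to about 2.1. Pooled power is then 0.58 to 0.82 at one intensity, and 0.60 to 0.99 for the three-intensity average. These ranges rest on assumed values of r (0 to 0.5) and c (0 to 0.9), on ± being an SD, and on zero control effect; the loss shrinks as the control effect grows. The plan should be corrected on these points, but nothing here shows that more swimmers are needed.

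**What to change.** - Replace the fixed-effects calculation with power for the within-swimmer cetirizine-minus-placebo contrast at a stated SD, over a range of placebo-cetirizine correlations, for 8 and for 12 swimmers and over a range of control effects. Putting f = 0.83 into the same routine would not do, because it keeps the independence assumption.
- State how f = 1.22 was obtained and what ± means in Table 2.
- State before unblinding whether the four controls enter the Aim 2 model. If they do, also report the effect in the eight selected swimmers, for example through a cohort × treatment term.

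The cost is SAP wording and one rerun of the calculation, with no extra swimmers or visits. The power statement becomes less simple, and the interaction will be imprecise with four controls: its single-intensity power is only about 0.41 (r = 0) to 0.69 (r = 0.5), even if the controls have no effect at all. The term therefore serves to estimate the effect in the eight, not to test whether the cohorts differ.
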